7.3 WITHDRAWAL OF SUBJECTS FROM STUDY TREATMENT AND/OR STUDY

The investigator and/or the subject have the right to terminate the subject's participation in the study at any time. Subjects who discontinue study drug should complete the Post-Treatment Safety Assessment visit.

A subject **may** withdraw (or be withdrawn) from the study treatment prematurely for any of the following reasons:

- Principal investigator (PI) determines further participation is not in subject's best interest.
- Clinically significant disease progression.

NOTE: In the absence of rapid clinical deterioration, disease progression should be confirmed by a repeat, consecutive assessment no less than 4 weeks from the date first documented to ensure that more slowly declining tumor burden in response to therapy is not missed.

A subject **MUST** be withdrawn in the event of any of the following:

- Withdrawal of informed consent. (Note: Any subject who wishes to withdraw from the study treatment may do so but will be counseled that follow-up for the effects of immunotherapy is strongly recommended.)
- Any DLT meeting the withdrawal criteria described in [Section 6.2.4](#).
- Any treatment-related adverse event meeting withdrawal criteria as described in [Section 8.2.6](#).
- Substantial noncompliance with the requirements of the study.
- Subjects with a confirmed positive pregnancy test (to be reported via pregnancy notification form).
- Any intercurrent illness that would, in the judgement of the investigator, affect assessments of clinical status to a significant degree and require discontinuation of protocol therapy.

Every effort should be made to follow subjects who withdraw from study treatment with ongoing treatment-related adverse events in order to determine the outcome of the event.

7.4 REPLACEMENT OF SUBJECTS

Subjects who are withdrawn from study treatment prior to completing Cycle 1 dosing for reasons other than toxicity may be replaced so that a full cohort of subjects completes Cycle 1 safety evaluations. In addition, should a subject discontinue study treatment before receiving 3 cycles for reasons other than toxicity, another subject may be added to that dose cohort so as to result in a total of at least three subjects for full analysis.

7.5 PREMATURE TERMINATION OF STUDY/CLOSURE OF CENTER

The sponsor has the right to close the study at any time, although this should occur only after mutual consultation between the sponsor and the investigators. The IRB/IEC must be informed. Should the study/center be closed prematurely, all study materials (completed, partially completed, and blank case report forms, study medication, etc) must be stored or disposed of according to the sponsor's instructions. Events that may trigger premature termination of the study or closure of a center include, but are not limited to a new toxicity finding, results of any interim analysis, noncompliance with the protocol, change in development plans for the study drug, slow recruitment, or poor-quality data.

8. TREATMENT PROCEDURES

8.1 SCREENING

Principal investigators (PIs) at each site are responsible for maintaining a record of all subjects screened, including both those who enter the study and those who are excluded.

8.1.1 Informed Consent

Each potential subject must sign a written, informed consent form (ICF) prior to performing any study specific screening procedure.

8.1.2 Inclusion and Exclusion Criteria

Inclusion and exclusion criteria will be reviewed for each potential subject and documented in the CRF.

8.1.3 Registration of Subjects

Centralized registration of subjects will be completed according to a process defined by the sponsor. The sponsor will assign a subject specific identification number and note the dose cohort to which the subject is assigned. Once assigned, a subject's identification number will not be reused.

8.2 STUDY DRUG

8.2.1 Accountability and Dispensation

The Principal Investigator (PI) must maintain accurate records accounting for the receipt and dispensation of the study drugs.

The investigational materials are to be prescribed only by the PI or the sub-investigators named on the Form FDA 1572, and may only be dispensed by authorized personnel at the institution(s) listed therein.

Under no circumstances will the PI allow investigational drug to be used other than as directed by the protocol.

8.2.2 Handling and Storage

Study drugs must be stored in a restricted access area under the storage conditions indicated on the product label or Investigator's Brochure.

All necessary precautions while handling potentially toxic compounds must be strictly followed.

8.2.3 Treatment Regimen

Each subject's assigned INXN-1001 dose will be given orally daily for the first 7 consecutive days of each 21-day cycle (Phase I and Phase II Group 1). For Phase II Group 2 the INXN-1001 dose will be given orally every other day for 14 days of each 28-day cycle,

INXN-2001 will be given as intratumoral injections of [REDACTED] in 0.5 mL per treatment. Following Cycle 1, if no accessible lesion for INXN-2001 injection is present (eg, due to complete resolution), then INXN-2001 should be injected into a tumor-involved

draining lymph node of a previously accessible lesion. The injections will be administered on the first day of each cycle throughout the study.

Subjects must be instructed to maintain adequate oral hydration on and in between dosing days; sites must closely monitor subjects' hydration status. [REDACTED]

[REDACTED] Blood pressure should be monitored Cycle 1 and 2 Days 1, 2, 3 or 4, and regularly thereafter.

8.2.4 Method for Assigning Subjects to Dose Level Cohorts

Subjects will be centrally assigned to dose level cohorts in accordance with the dose escalation scheme for this study.

8.2.5 Preparation and Administration of Study Drug

A combination of two investigational medications will be evaluated for safety, tolerability, efficacy, and biological effects in this trial. The small molecule INXN-1001 will be administered as oral capsules to subjects in combination with an intratumoral injection of INXN-2001 (on Day 1 of each cycle). For each treatment cycle, INXN-2001 dosing will occur 3 hours \pm 30 minutes after the first dose of INXN-1001.

8.2.5.1 Preparation and Administration of INXN-1001

INXN-1001 will be provided by the sponsor in gelatin capsules of three different strengths (5 mg, 10 mg and 20 mg).

INXN-1001 capsules will be dispensed for subject oral dosing by the site pharmacy. The site must instruct the subject to take each dose in a fed state (30 minutes after the start of a normal meal) and to not eat any food for at least 4 hours after each dose is taken.

8.2.5.2 Monitoring of Subject Adherence and Managing Missed INXN-1001 Doses

The first daily dose of INXN-1001 at each treatment cycle is expected to be administered to the subject at the clinical site, under careful medical supervision by the clinic staff to ensure that the subject does not have difficulty with the size or quantity of capsules to be administered. Thereafter, subjects may be allowed to self-administer the remaining 6 doses at approximately the same time and in the same relationship to meals as administered at the clinical site on Day 1 of the treatment cycle. Subjects are to be instructed to take all of the capsules in the same way for the remaining treatment period.

Subjects should be instructed to make up for a missed dose by taking the dose the following day, and then continuing with dosing as scheduled (eg, if the dose on Day 3 is missed, dosing should occur on Day 4 and then continue as scheduled on Days 5, 7, 9 etc.).

Subjects will also be instructed to bring the treatment container(s) back with all remaining capsules at the next visit, to provide an assessment of the degree of adherence. All subjects will be queried about dose schedule adherence and reasons for missed doses.

8.2.5.3 Preparation and Administration of INXN-2001

INXN-2001 will be supplied by the sponsor as single dose vials. Information regarding the preparation of the INXN-2001 dose will be provided in the Pharmacy Manual.

INXN-2001 [REDACTED] will be administered as an intratumoral injection 3 hours (\pm 30 minutes) after oral INXN-1001 dosing on Day 1 of each cycle. INXN-2001 should be injected into a different lesion at each cycle.

If only 3 accessible lesions are present, the injections will be done in sequential rotation between 2 lesions. If only 2 accessible lesions are present, then all injections will be into a single lesion. If only 2 accessible lesions are present at screening and the single injected lesion can no longer support the injection volume at subsequent cycles, then the medical monitor should be contacted for a discussion.

Note: One accessible lesion will not be injected since that lesion will be used to evaluate the systemic effect of INXN-2001.

The INXN-2001 intratumoral administration should be delivered by multiple injections with a fine needle (no finer than 27 gauge) directly into each quadrant of the lesion or tumor-involved lymph node, at approximately 0.5 cm apart three dimensionally, to reach all aspects of the entire lesion. Attention must be paid to adequately infiltrate the circumference of the tumor margins. Radiographically-guided injections are permitted under BL2 conditions. A detailed description and photograph of physical location(s) of the injected tumor(s) and surrounding tissue, and any visible local reactions should be documented. Lesions displaying signs of local infection should not be injected.

Should the tumor selected for injection not support the entire INXN-2001 injection volume, another tumor should be injected with the remaining volume to ensure that all subjects receive [REDACTED]. If another tumor is not available, then the remaining volume should be injected into a draining lymph node of the injected tumor. Following Cycle 1, if no accessible lesion for INXN-2001 injection is present (eg, due to complete resolution), then INXN-2001 should be injected into a draining lymph node of a previously accessible lesion.

Each subject will be carefully monitored for possible local reactions at the injection site and/or hypersensitivity reactions, for at least 2 hours following the INXN-2001 injection. The subject should be instructed to call the clinical site if any such reactions develop or don't resolve within 24 to 48 hours.

8.2.6 Retreatment Criteria, Dose Delays and Modifications

Subjects may receive up to 6 cycles of study drug treatment. In order to receive each repeat treatment cycle, all treatment-related adverse events must have resolved to Grade 1 or baseline and the following laboratory criteria must be met:

- Hemoglobin ≥ 9 g/L
- Lymphocytes $> 700/\text{mm}^3$
- Neutrophils $\geq 1,500/\text{mm}^3$
- Platelets $\geq 100,000/\text{mm}^3$
- Serum creatinine $\leq 1.5 \times \text{ULN}$
- AST and ALT $\leq 2.5 \times \text{ULN}$. For subjects with documented liver metastases, ALT and AST $\leq 5 \times \text{ULN}$
- Total bilirubin $< 1.5 \times \text{ULN}$
- INR and PTT $< 1.5 \times \text{ULN}$, if not therapeutically anticoagulated.

Clinical laboratory tests drawn for analysis on Day 15 of each cycle may be used for determining if the retreatment criteria have been met, and must be reviewed by the investigator or designee prior to the next cycle of study drug administration. Treatment delays to allow for recovery to acceptable levels are allowed at weekly intervals up to a maximum of 4 weeks. In the event that a treatment-related dose delay is necessary, then the next cycle of study treatment will be administered at the next lower INXN-1001 dose level. Subjects in the first dose cohort who do not meet the retreatment criteria will be discontinued from study treatment (ie, no dose reductions are permitted).

Subjects who experience a DLT will be managed as described in [Section 6.2.4](#). Subjects who experience an injection site reaction should be managed as described in [Section 8.2.7](#).

Subjects who experience a treatment-related Grade 3 adverse event, other than nausea and/or vomiting in the absence of optimal treatment with anti-emetics, will be discontinued from study treatment. If, however, the subject has experienced a substantial benefit from treatment and the SRC recommends continuation on the study, re-exposure to the experimental treatment may proceed on a case by case basis.

Subjects who experienced a Grade 4 treatment-related adverse event at any time during study treatment must be discontinued from study treatment.

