7.1 INCLUSION CRITERIA

To be enrolled in the trial, each subject must satisfy all of the following inclusion criteria:

1. Males or females of all races \geq 18 years of age, who have provided written informed consent prior to completing any study specific procedure.
2. Unresectable Stage III or Stage IV melanoma arising from any site other than ocular melanoma.
3. A minimum of 2 accessible lesions (shortest diameter \geq 1 cm) or palpable tumor-involved lymph nodes (shortest diameter \geq 1.5 cm).

4. ECOG performance status of 0 or 1 ([Appendix 1](#)).
5. Adequate bone marrow, liver, and renal function, as assessed by the following laboratory requirements:
 - a. Hemoglobin \geq 9 g/L
 - b. Lymphocytes $> 700/\text{mm}^3$
 - c. Neutrophils $\geq 1,500/\text{mm}^3$
 - d. Platelets $\geq 100,000/\text{mm}^3$
 - e. Serum creatinine $\leq 1.5 \times \text{ULN}$
 - f. AST and ALT $\leq 2.5 \times \text{ULN}$. For subjects with documented liver metastases, ALT and AST $\leq 5 \times \text{ULN}$
 - g. Total bilirubin $< 1.5 \times \text{ULN}$
 - h. International Normalized Ratio (INR) and activated partial thromboplastin time [PTT] $< 1.5 \times \text{ULN}$, if not therapeutically anticoagulated. Subjects who are being therapeutically anticoagulated with an agent such as Coumadin (warfarin sodium) or subcutaneous heparin may be included provided there is no prior evidence of underlying abnormality in coagulation parameters, screening test results are in appropriate therapeutic range, and anticoagulation regimen is stable and closely monitored.
6. An expected survival of at least 6 months.
7. Male and female subjects must agree to use a highly reliable method of birth control (expected failure rate less than 5% per year) from the screening visit through 28 days after the last dose of study drug.

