6.0 Patient Disposition

6.1 Sample Size

No formal sample-size estimation was performed.

Thirteen patients were treated in Phase I and 13 patients were treated in Phase II.

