7.0 Protocol Deviations

Protocol deviations are defined as those deviations from the study protocol that may have the ability to impact the results.

No patient will be removed from any analysis population because of a protocol deviation. Protocol deviations were partially collected on the CRF. A further review of the data will be conducted to identify any of the following:

- Deviation from inclusion/exclusion criteria
- Withdrawal criteria met during the study but patient was not withdrawn
- Use of prohibited concomitant medications.

Where possible the first two items will be checked programmatically. For prohibited medications, a spreadsheet of the coded terms will be provided for the sponsor to review.

All protocol deviations including those not databased will be listed.

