12.3 Laboratory Evaluations

Laboratory data for blood chemistry, hematology, and urinalysis will be collected throughout the study.

The following laboratory tests are to be performed as indicated by the schedule of assessments:

| Blood Chemistry | Hematology | Urinalysis |
|----------------------------|--------------------------------|--------------------|
| Albumin | Basophils | Appearance |
| Alanine aminotransferase | | pH |
| Alkaline phosphate | Eosinophils | Specific gravity |
| Aspartate aminotransferase | Platelets | Glucose |
| Bicarbonate | Red blood cell (RBC) | Protein/Albumin |
| Total bilirubin | Hepatitis C Virus | RBC Hgb |
| Blood urea nitrogen | Hemoglobin (Hgb) | Ketones |
| Calcium | Hematocrit | Bilirubin |
| Chloride | International Normalized Ratio | Nitrates |
| Creatinine | Mean corpuscular volume | Leukocyte esterase |
| Gamma glutamyl transferase | Mean corpuscular hemoglobin | |
| Glucose | Neutrophils | |
| Lactic dehydrogenase | Partial thromboplastin time | |
| Potassium | Reticulocytes | |
| Phosphorus | White blood cell | |
| Sodium | | |
| Total protein | | |

Shift tables will be constructed for the clinical chemistry and hematology data showing the shift from the baseline value to the worst (minimum or maximum value) post baseline.

The absolute value and the change from baseline will be tabulated for each scheduled time-point during the study for all continuous urinalysis parameters. Baseline is defined as the Screening value.

Details of clinical chemistry and hematology data will be listed including converted values and showing reference ranges and flagging of abnormal findings and their clinical significance. Out of reference range values will be flagged as high (H) or low (L) in the listing. Laboratory reference ranges will be presented by site.

Pregnancy test details at Screening (serum) and Day 1 of each cycle (urine) will be listed.

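### The hemoglobin limit for entry and for each repeat cycle is printed as 9 g/L (0.9 g/dL), evidently meant as 9 g/dL, and read literally it excludes no one

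*Protocol*

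**What the plan says.** Protocol Section 8.2.6 lists "Hemoglobin ≥ 9 g/L" among the laboratory conditions for each repeat cycle. The same value and unit stand in criterion 5a of the inclusion criteria, both in Section 7.1 and in the Synopsis, where the stated purpose is to establish adequate marrow, liver and kidney function. Section 8.2.6 adds a separate condition, that "all treatment-related adverse events must have resolved to Grade 1 or baseline".

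SAP Section 7.0 names "Deviation from inclusion/exclusion criteria" as the first of three deviation types to look for and says: "Where possible the first two items will be checked programmatically". The second type is meeting a withdrawal criterion without being withdrawn; failing a retreatment criterion is not named. The section also states: "No patient will be removed from any analysis population because of a protocol deviation".

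SAP Section 12.3 includes hemoglobin among the hematology tests and says: "Details of clinical chemistry and hematology data will be listed including converted values". It gives no unit for hemoglobin and no threshold.

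**The concern.** A limit of 0.9 g/dL cannot serve as a test of adequate marrow function, so the unit is almost certainly wrong. The line matters because it is an operative decision rule, used once at entry and again before every repeat cycle.

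Two things are at stake. The first is the safety threshold: read as printed, no fixed hemoglobin limit remains for a subject who is already anemic at screening, or for anemia during the study that is attributed to something other than treatment. The second is the deviation reporting (Table 14.1.2 and Listing 16.2.2). A program that checks eligibility needs a number and a unit, and the only ones the documents supply are the misprinted ones.

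**Working it through.** **Inputs**
- Printed limit: 9 g/L (Protocol Synopsis; Section 7.1, criterion 5a; Section 8.2.6).
- Evident limit: 9 g/dL. This is an inference from the purpose of the criterion; neither document states it.
- Treated patients: "Thirteen patients were treated in Phase I and 13 patients were treated in Phase II" (SAP Section 6.1).
- Maximum cycles per patient: 6 (Protocol Section 8.2.6).

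**Conversion.** 1 dL = 0.1 L, so g/L ÷ 10 = g/dL.
- Printed limit: 9 ÷ 10 = 0.9 g/dL.
- Evident limit: 9 × 10 = 90 g/L.
- Ratio: 90 ÷ 9 = 10.

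**Both limits applied to a range of values.** The range of 3 to 15 g/dL is assumed; the documents give no hemoglobin data.

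| Hemoglobin, g/dL | Hemoglobin, g/L | Passes 9 g/L | Passes 9 g/dL |
|---|---|---|---|
| 3 | 30 | yes | no |
| 5 | 50 | yes | no |
| 7 | 70 | yes | no |
| 8 | 80 | yes | no |
| 8.9 | 89 | yes | no |
| 9 | 90 | yes | yes |
| 10 | 100 | yes | yes |
| 12 | 120 | yes | yes |
| 15 | 150 | yes | yes |

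Every value tested passes the printed limit. The two limits disagree for hemoglobin from 9 to below 90 g/L.

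**Number of decisions governed by the limit**
- Entry: 13 + 13 = 26.
- Repeat cycles: 6 − 1 = 5 per patient at most, so no more than 26 × 5 = 130. This is a ceiling. Section 6.2.1 says earlier subjects received 3 cycles, so the real number is lower.
- Patients between the two limits: not given; anywhere from 0 to 26.

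**What an eligibility program would do**
- Values in g/L, limit coded as printed (9): flags no one, provided no patient is below 0.9 g/dL.
- Values in g/L, limit coded as 90: flags the intended patients, but against a limit the protocol does not print.
- Values in g/dL, compared with 9 without regard to the printed unit: gives the intended result, but only because the unit was ignored.

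The documents do not say which of these applies.

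**What still works if the line is read literally**
- The lymphocyte, neutrophil and platelet limits remain, but they concern other cell lines.
- The rule on resolution of treatment-related events still covers treatment-related anemia. It refers back to baseline, however, so a subject admitted with a low hemoglobin meets it by returning to that low value.
- Exclusion 11 can keep out a subject with a significant medical condition at entry, but it depends on the investigator's opinion.

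**The case against.** The strongest reply is that this is a misprint which corrects itself. No clinician would take 0.9 g/dL as a working limit, and sites very probably applied 9 g/dL. Other controls overlap with it:
- registration is central and the sponsor approves participation;
- Day 15 laboratory results, if used for retreatment, must be reviewed before the next cycle;
- Section 7.3 lets the investigator stop treatment in the subject's interest and requires withdrawal for certain intercurrent illnesses;
- Section 9.2.3 reserves the unrelated category for events clearly caused by something else, so doubtful anemia falls under the rule for treatment-related events.

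On the SAP side, programmed checking is only where possible, deviations are also partly collected on the CRF, and low hemoglobin would be visible in the hematology listing and the shift table. The 26 patients have already been treated, so amending the protocol changes no past decision.

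Much of this stands. It makes harm unlikely, narrows the uncovered group, and keeps the point well short of a threat to the trial's conclusions. It does not remove the error. Central registration applies the same misprinted criterion, and the remaining controls rest on judgement; none restores a fixed hemoglobin limit for anemia at entry or anemia unrelated to treatment. Nor does a listing of laboratory values say which limit the deviation table used. SAP Section 12.3 gives no reporting unit for blood chemistry or hematology tests generally, so the missing hemoglobin unit there is a detail, not a separate fault.

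**Conclusion.** The concern holds. The hemoglobin limit is wrong as written in all three operative places, by a factor of ten, and read literally that single limit excludes no one. It governs 26 entry decisions and at most 130 retreatment decisions. The consequence is confined to the safety threshold and to the reporting of eligibility deviations. It does not reach the analysis populations, because deviations remove no one from them, or the efficacy summaries.

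This rests on two assumptions: that g/dL was the intended unit, and that no treated patient had hemoglobin below 0.9 g/dL. The documents do not show that any site used the limit literally, and the number of patients affected is unknown. The correction should be made because the text is wrong and the cost is very small, not because harm has been shown.

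**What to change.** Subject to sponsor confirmation, change the unit to g/dL (9 g/dL, equal to 90 g/L) in the Synopsis, Section 7.1 criterion 5a and Section 8.2.6, by amendment or clarification note.

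In SAP Section 7.0, add one sentence giving that value and unit as the limit for the eligibility deviation check. This is the part that still has practical effect: it cannot alter decisions already made, but it makes Table 14.1.2 and Listing 16.2.2 interpretable for this criterion. Stating the hemoglobin reporting unit in SAP Section 12.3 would help, but is secondary.

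The cost is three unit corrections and one or two sentences in the SAP. Populations, sample size and efficacy analyses are unchanged.
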